
Study Design:
 
This is a Phase 1, randomized, double-blind, placebo-controlled, single- and multiple-dose ascending study in healthy subjects with concurrent PK sampling from blood plasma, urine, and cerebrospinal fluid. The overall study design is outlined below:
 
Part 1: Single-Dose Regimen and Fasted-Fed Crossover
 
For the single-dose regimen, approximately 40 healthy male or female subjects will be enrolled in 1 of 5 single-dose cohorts (designated as S1 through S5, respectively) in an ascending fashion. An optional 8 subject (Cohort S3a) may be added in parallel with Cohort S3. Cohort S3a dose level will be consistent with Cohort S3 (45 mg planned) in a fasted condition only and without lumbar puncture, aligned with the Schedule of Procedures (Appendix A) and other SAD Cohorts. Each cohort will consist of 8 subjects randomized to CVN766 or placebo. In each cohort, 6 subjects will receive a single oral dose of CVN766 suspension, and 2 subjects will receive a matching placebo suspension under overnight fasted conditions. Subjects will remain fasted for 4 hours post-dose. Consumption of water is permitted as desired except for 1 hour before and after administration of Study Drug. Sentinel dosing (1 subject to receive CVN766 and 1 subject to receive placebo) will be used in each cohort to ensure adequate safety and tolerability evaluation prior to administering CVN766 or placebo to the remainder of the subjects within the cohort. After blinded review by the Investigator of 24-hour post-dose adverse event listings (as applicable) from the sentinel group, the Investigator will advise the sponsor on the acceptability of enrolling the remaining 6 subjects in each cohort. In the event that a safety signal emerges in the sentinel group, a Safety Review Group (SRG) meeting may be required as requested by Investigator or Sponsor. To accommodate the lumbar puncture in the S3 fasted cohort, the remaining 6 subjects' dosing may be staggered every two days after the sentinel group. The planned dose levels will be 5, 15, 45, 125, and 250 mg CVN766. The SRG will review all available blinded safety, tolerability, clinical laboratory results (minimally including samples collected from subjects through 72-hours post-dose), and available pharmacokinetic (PK) data prior to all dose escalations and after the completion of all subjects in a cohort. If Cohort S3a (optional cohort) is enrolled and completed prior to Cohort 3, the SRG may determine dose escalation to Cohort S4 after evaluating data from Cohort 3a alone. Each following dose level may be higher, lower, or remain the same as the preceding cohort, dependent on the recommendation of the SRG.
 
Additional cohort(s) may be added if deemed necessary by the SRG to fully characterize the safety and tolerability
		

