
clinical laboratory results from a minimum of 5 subjects in the current cohort),
 
 2. Escalate to the next planned cohort or alternative dose levels (e.g., lower, intermediate, or higher) in multiple-dose cohorts (based on a review of available data, including at least 48 hours post 7th dose safety data from a minimum of 5 subjects in the current cohort), 3. Add additional dose cohort(s) in either the single- or multiple-dose studies, 4. Increase the duration of dosing in the multiple-dose cohorts from 7 days to ≤ 14 days, 
In addition, if 2 or more subjects in a single cohort experience the same type of serious or medically significant event, further dosing will be withheld until the SRG investigates the events. Based on this assessment, the SRG will determine if the study should be terminated or continued and whether modification of planned dose levels and/or implementation of additional safety monitoring is indicated.
	

Primary Objective:
 
To characterize the safety and tolerability profile of escalating dose levels of CVN766 suspension when administered as a single oral dose or daily oral doses for 7 days in healthy subjects and determine the recommended phase 2 dose (RP2D).
	

Secondary Objectives:
 
 • To characterize the single-dose PK profile of CVN766 in plasma and CSF • To characterize the multiple-dose PK profile of CVN766 in plasma and CSF • To assess the effect of food on the bioavailability of CVN766 	

Exploratory Objectives:
 
 • To explore possible drug metabolic enzyme and transporter polymorphisms that may contribute to variability in CVN766 PK, pharmacodynamics, or safety 	

Subject Population: Healthy male and female subjects 18 to 55 years old
	

Number of Subjects:
 
Each dose cohort: 8 subjects (6 active:2 placebo) Estimated total: 64 subjects (5 single-dose cohorts, 3 multiple-dose cohorts)
	
Number of Sites:
 
2 (Australia)

Dose Level(s):
 
Planned single-dose levels are placebo, 5 mg, 15 mg, 45 mg, 125 mg, and 250 mg CVN766. Planned multiple dose levels are placebo, 45 mg, 125 mg, and 250 mg CVN766.
	
Route of Administration:
 
Oral

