
Duration of Treatment:
 
Single or daily oral doses for up to 7 days (+7 days as necessary to reach steady-state and as required by Safety Review Group).
	
Period of Evaluation:
 
Screening Period: up to 28 days Treatment Period: 1-7 days (+7 days, as necessary). Food Effect washout period (for select cohort only): at least 14 days Follow-up Period: approximately 14 days Total Duration:
 
 • Single-dose cohorts: approximately 6 weeks • Food effect cohort: approximately 8 weeks • Multiple-dose cohorts: approximately 7 weeks

Main Criteria for Inclusion:
	

Healthy male and female subjects who are 18 to 55 years of age, inclusive and have a body mass index (BMI) between 18.0 and 32.0 kg/m² inclusive at Screening.

A complete list of inclusion criteria is provided in **Section 7.1**.

Main Criteria for Exclusion:

Subjects have a known hypersensitivity to any component of the formulation of CVN766. Subjects have evidence of CS neurologic, cardiovascular, pulmonary, hepatic, hematopoietic disease, renal, metabolic, gastrointestinal, urologic, immunologic, endocrine disease, serious allergy, allergic skin rash, psychiatric disorder, or other abnormality that may impact the ability of the subject to participate or potentially confound the study results. Any finding in the subject's medical history, physical examination, or safety laboratory tests gives reasonable suspicion of a condition that might interfere with the conduct or interpretation of the study.

A complete list of exclusion criteria is provided in **Section 7.2**.

In addition, subjects may not use any excluded medications (including oral contraceptives as listed in Table 3), supplements, or food products. Concomitant medications and dietary products to be excluded are listed in Table 3.

Main Criteria for Evaluation and Analyses:

- Safety:

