6.1.2 Part 2: Multiple-Dose Regimen

For the multiple-dose regimen, approximately 24 subjects will be enrolled in 1 of the 3 multiple-dose cohorts (designated as M1 through M3, respectively) in an ascending fashion. Dosing will be administered in the fasting state; this can be changed by the SRG if exposure is found to be higher in the fed state. The dose levels planned to be studied in the multiple-dose regimen (M1 through M3) are provided in **Table 5**. Each multiple-dose cohort will consist of 8 subjects randomized to CVN766 or placebo, whereby 6 subjects will receive a daily dose of CVN766, and 2 subjects will receive matching placebo for 7 days. However, the duration may be increased to ≤14 days at the discretion of the safety review group (SRG) if preliminary PK data suggest steady-state will not be achieved within 6 days of daily dosing. Unlike the single-dose regimen, sentinel dosing within cohorts is not required in the multiple-dose regimen.

Subjects for all multiple-dose cohorts will be admitted to the study unit 1 day prior to dosing and remain in the unit for the duration of the dosing period and for at least 48 hours after the last dose for safety and PK assessments before discharge. On treatment Days 1 and 7, subjects will undergo safety monitoring and PK sampling from blood plasma through 48 hours post-dose and, in Cohort M1 only, from urine through 24 hours post-dose. In Cohorts M1 and M2, on treatment Day 7 (or last day of dosing, if extended beyond Day 7), subjects will undergo additional PK sampling from CSF via lumbar puncture at 3 hours post-dose. If the SRG determines additional PK sampling from CSF via lumbar puncture is not necessary for Cohort M2, the lumbar puncture may be omitted. Likewise, if needed to resolve questions arising from prior Cohorts’ data, subjects in Cohort M3 also may, at SRG discretion, undergo PK sampling from CSF via lumbar puncture, the choice of day (e.g., Day 1 or Day 7) and sampling time to be decided by SRG. Subjects in MAD cohorts may be asked to return to the clinic for an additional plasma PK sample 3 days after the last dose (e.g., Day 10) depending on emerging PK data, i.e., $t_{1/2}$. The total confinement period will be 9 nights unless extended for additional dosing days or management of AEs. Follow-up assessments will occur approximately 7 and 14 days after the final dose. A summary of multiple-dose study visits is included in **Appendix A**.

Table 2 Multiple Dose Visit Schedule

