6.1.3 Dose Escalation

The SRG will comprise the Investigator, Medical Monitor, Cerevance Responsible Medical Officer and may include other Cerevance representatives. A pharmacokineticist and other subject matter experts may participate as needed. The SRG will be responsible for the ongoing review of safety, tolerability, clinical laboratory results, and available PK data and deciding to:

- Escalate to the next planned cohort or alternative dose levels (e.g., lower, intermediate, or higher) in single-dose cohorts (based on a review of available data, including at least 72 hours post-dose safety data and clinical laboratory results from a minimum of 6 evaluable subjects in the current cohort),
- Escalate to the next planned cohort or alternative dose levels (e.g., lower, intermediate, or higher) in multiple-dose cohorts (based on a review of available data, including at least 48 hours post 7th dose safety data from a minimum of 6 evaluable subjects in the current cohort),
- Add additional dose cohort(s) in either the single- or multiple-dose studies,
- Increase the duration of dosing in the multiple-dose cohorts from 7 days to ≤14 days

If 2 or more subjects in a single cohort experience the same type of serious or medically adverse event, further dosing will be withheld until the SRG investigates the events. Based on this assessment, the SRG will determine if the study should be terminated or continued and whether modification of planned dose levels and/or implementation of additional safety monitoring is indicated.

For each cohort (including sentinel subjects, where applicable), the SRG will carefully review the available blinded safety, tolerability, clinical laboratory results, and available PK data to determine whether dosing should stop or continue (and, if continued, at what dose, including whether to repeat the previous dose), whether additional sequential dosing should be implemented in future cohorts or whether the blind should be broken to identify whether the subjects received CVN766 or placebo. However, precautions must be taken not to unblind the study staff, including the Investigator.

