7.6 Procedures for Discontinuation or Withdrawal of a Subject

The Investigator must discontinue a subject’s study participation at any time during the study when the subject meets the study discontinuation criteria described in **Section 7.5**. In addition, a subject may discontinue their participation without giving a reason at any time during the study. Should a subject’s involvement be terminated, the primary criterion for termination must be recorded by the Investigator. In addition, efforts should be made to perform all procedures scheduled for the Early Termination Visit. Discontinued or withdrawn subjects may be replaced at the Sponsor’s discretion.

Participants who withdraw from the study prior to dosing may be replaced. If a participant withdraws after the first dose of study medication or placebo, no replacement will occur.

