9.3.3 Final Visit (discharge day from clinic)

Subjects will be confined to the study clinic for the duration of the treatment period to permit supervised dosing of study drug and repeat study assessments. Subjects participating in the single-dose study and food effect assessment will be discharged no sooner than 72 hours post-dose, and subjects participating in the multiple-dose study will be discharged no sooner than 48 hours following their last dose.

For all subjects receiving study medication, the Investigator must complete the End of Study eCRF page.

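### The multiple-dose escalation minimum stays at 48 hours after the 7th dose even if dosing is extended to as many as 14 days

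*Protocol*

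**What the plan says.** Section references are to the later of the two protocol versions in the file (two sites, optional Cohort S3a).

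**The escalation minimum.** Section 6.1.3 requires "at least 48 hours post 7th dose safety data from a minimum of 6 evaluable subjects in the current cohort". The Safety Review Group part of the synopsis (Section 2.0) requires "at least 48 hours post 7th dose safety data from a minimum of 5 subjects in the current cohort". The subject counts differ, which is a separate matter. The time point is the same.

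**The extension.** The same two lists give the SRG power to lengthen dosing from 7 days to as many as 14. Section 6.1.2 ties this to the case "if preliminary PK data suggest steady-state will not be achieved within 6 days of daily dosing", and the synopsis row on treatment duration allows a further "7 days as necessary to reach steady-state and as required by Safety Review Group".

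**What follows the last dose.**
- CSF sampling is "on treatment Day 7 (or last day of dosing, if extended beyond Day 7" (Section 6.1.2).
- Multiple-dose subjects are "discharged no sooner than 48 hours following their last dose" (Section 9.3.3).
- The synopsis text for Part 2 and Section 7.4 define the intensive PK days as the first and last dosing days, with Days 1 and 7 as examples.
- Table 2 times the later visits in days after the last dose.
- The Appendix A columns are labelled by last dose, with Days 7 to 9 as examples.

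**What is literally numbered Day 7.** This covers Table 7, urine sampling (Table 2, note f) and notes c and h of the multiple-dose schedule in Appendix A.

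**The concern.** Under 7-day dosing, the minimum guarantees 48 hours of safety data after treatment ends before the next dose level is cleared. The single-dose rule does the same with 72 hours after the only dose. An extension removes that guarantee, because the last dose moves and the minimum does not.

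The extension is meant for a drug that has not reached steady state within 6 days, so exposure may still be rising after the 7th dose. Multiple-dose cohorts also need no sentinel subjects (Section 6.1.2), so the review between cohorts carries more of the protection. At stake is whether the next step, from 45 to 125 mg or from 125 to 250 mg, could be cleared within the rules while the current cohort is still being dosed.

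**Working it through.** **1. The plan's own figure.** Dose k is given on Day k. The minimum is Day 7 + 2 = Day 9, which is also the planned discharge day under 7-day dosing (Table 2, note b). For 7-day cohorts the rule is consistent.

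**2. With an extension.** For a last dosing day N, 48 hours after the last dose is Day N + 2. The shortfall is (N + 2) − 9 = N − 7 days. Doses still to come on Day 9 number N − 8 before that day's dose and N − 9 after it (not below 0).

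| Dosing days N | Written minimum | 48 h after last dose | Shortfall (days) | Doses to come before / after the Day 9 dose |
|---|---|---|---|---|
| 7 | Day 9 | Day 9 | 0 | 0 / 0 |
| 8 | Day 9 | Day 10 | 1 | 0 / 0 |
| 9 | Day 9 | Day 11 | 2 | 1 / 0 |
| 10 | Day 9 | Day 12 | 3 | 2 / 1 |
| 12 | Day 9 | Day 14 | 5 | 4 / 3 |
| 14 | Day 9 | Day 16 | 7 | 6 / 5 |

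At N = 8 the minimum falls 24 hours after the last dose. At N = 9 it falls on the last dosing day. From N = 10 it falls while dosing continues.

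**3. Does other text move the minimum?**
- The synopsis says the SRG reviews data "prior to all dose escalations and after the completion of all subjects in a cohort", but this stands in the Part 1 text and completion is not defined.
- Section 6.1.3 requires a full review of the preceding cohort, but of available data. It also requires the M1 and S4 reviews to be complete before M2 starts, without setting a time after the last dose.
- Its review of adverse events up to discharge concerns subject or study termination.
- The stopping rules in Section 6.3.1 react to events and set no minimum amount of data.

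None of these supplies a cut-off tied to the last dose.

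**4. How much exposure is at issue?** The protocol gives no human half-life, so this step is an assumption: linear one-compartment kinetics, dosing every 24 hours, half-life t in hours. The fraction of steady state after n doses is 1 − 2^(−24n/t). The ratio of dose 14 to dose 7 is (1 − 2^(−336/t)) / (1 − 2^(−168/t)) = 1 + 2^(−168/t), so the excess is 2^(−168/t).

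The protocol uses both 4 half-lives (washout, Section 6.1.1) and 5 half-lives (elimination, Section 6.2), so both are shown.

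- *At the trigger* (steady state just reached in 6 days = 144 h): t = 144/5 = 28.8 h gives 2^(−5.83) = 1.75%. t = 144/4 = 36 h gives 2^(−4.67) = 3.94%.
- *At the longest half-life that 14 days (336 h) could bring to steady state*: t = 336/5 = 67.2 h gives 2^(−2.5) = 17.7%. t = 336/4 = 84 h gives 2^(−2) = 25.0%.
- *At the animal upper value* (6.5 h, Section 6.2): 2^(−25.8), which is 0.00%. No extension would be triggered.

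**The case against.** The strongest reply is that the 7th dose is shorthand for the planned last dose. The protocol mostly uses Day 7 as an example of the last dosing day, so a sensible SRG would read the minimum the same way. The SRG also decides both the extension and the escalation, the minimum is only a minimum, and subjects stay in the unit for 48 hours after their last dose. Each multiple-dose level will have been studied or exceeded as a single dose first (Section 6.2). The trigger needs a half-life of about 29–36 hours, more than four times the animal value.

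Most of this stands, and it limits the consequence. It does not repair the rule. The convention that makes the shorthand plausible also shows what is missing: elsewhere the protocol adds the last-dose alternative or marks Day 7 as an example, and here it names the 7th dose outright, twice.

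Three stronger readings are tempting and are not supported:

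- *That much of the safety and PK schedule stays at Day 7 in an extended cohort.* The synopsis and Section 7.4 make Days 1 and 7 examples of the first and last dosing days, and the Appendix A columns follow the last dose. The few items numbered Day 7 can be read in that light.
- *That the planned trial would escalate during dosing.* This needs an extension and an SRG that acts at the bare minimum. The three planned 7-day cohorts are not affected.
- *That the rule also needs a condition on which subjects count.* Section 7.6 does say "If a participant withdraws after the first dose of study medication or placebo, no replacement will occur", but the same section also allows replacement at the sponsor's discretion. Once the time point is the cohort's last scheduled dose, a separate condition is largely redundant.

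**Conclusion.** The point holds as a gap in the written rule. In a cohort extended beyond 7 days, the escalation minimum can be met without 48 hours of data after treatment, and from 10 days of dosing it can be met while doses remain. The shortfall is 1 to 7 days. This follows from day arithmetic and needs no assumption about the drug.

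The exposure figures do rest on assumed linear kinetics and half-lives that the protocol does not give. They are small near the trigger (about 2–4% for dose 14 over dose 7) and at most about 18–25% for half-lives that 14 days could bring to steady state. The main loss is therefore observation after the end of treatment rather than a large unseen rise in exposure.

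The gap arises only if the extension is used, which the animal half-life makes unlikely. It is worth correcting because the protocol deliberately provides for the extension and the correction is cheap.

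**What to change.** In the Safety Review Group list of the synopsis and in Section 6.1.3, replace the 7th-dose time point with: *safety data through at least 48 hours after the last scheduled dose of the cohort (the 7th dose, or the final dose if dosing is extended)*. Add no further evaluability condition.

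The cost is wording in two places. Seven-day cohorts still clear on Day 9. A cohort dosed for 8 to 14 days clears on Day 10 to Day 16, so the next cohort waits 1 to 7 days longer. That wait secures the same 48 hours of post-treatment observation that a 7-day cohort already gives.

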6.2 Justification for Study Design, Dose, and Endpoints

The study is double-blind and placebo-controlled to avoid subjective bias in assessing the safety and tolerability of CVN766. Dose escalation will be predicated on a review of available blinded safety, tolerability, and PK data from a minimum of evaluable 6 subjects from the prior Cohort.

The sponsor has selected the starting dose level considering the FDA Guidance for Industry (Estimating the Maximum Safe Starting Dose in Initial Clinical Trials for Therapeutics in Adult Healthy Volunteers, 06 July 2005) and providing additional safety factors to the initial calculations based on the principles outlined in the guidance. The toxicity profile of CVN766 after oral dosing was examined in repeat dosing studies in rats and dogs. Scaling based on body surface area was conducted by multiplying the NOAELs for the most sensitive animal species by the appropriate conversion factors. Based on these calculations and applying a 10-fold safety margin below the NOAEL human-equivalent dose (HED), the maximum recommended starting dose (MRSD) for this first-in-human study is 167 mg for a 60 kg subject. The selected starting dose level is 5 mg.

The study's multiple-ascending dose (MAD) portion seeks to prepare for subsequent repeat dosing studies in subjects. Each MAD dose level will have been studied or exceeded in the SAD portion of the study before its use in a MAD cohort.

Nonclinical toxicity study data provide a basis for calculating the maximum exposure level that can be presumed safe. Escalating to the HED of the NOAEL in the most sensitive animal species, the maximum dose for clinical use is 1670 mg/day.

The projected $t_{1/2z}$ in animal species ranged up to 6.5 hours, so sample collection through Inpatient Discharge 72 hours post-dose is expected to correspond to more than 5 half-lives and is anticipated to be adequate to document elimination of CVN766. The study design allows for collecting additional PK samples at later timepoints if preliminary emerging PK results are indicated.

AEs, physical exams, vital signs, ECG findings, and clinical laboratory results are used as safety assessments to determine dose tolerability and dose-limiting effects of CVN766. The plasma PK and CSF parameters and PK endpoints will help elucidate the pharmacology of CVN766.

Samples for DNA analysis will be collected and may be used to evaluate drug metabolic enzyme and transporter polymorphisms that may contribute to the variability in the PK of CVN766.

6.3 Premature Termination or Suspension of Study or Investigational Site

6.3.1 Criteria for Premature Termination or Suspension of the Study

The study will be completed as planned unless new information or other evaluation regarding the safety of the study medication indicates an adverse change in the risk profile for the compound, such that the SRG or Institutional Review Board (IRB) considers the risk is no longer acceptable for subjects participating in the study.

In addition, if any of the following occur, further dosing will be withheld until the SRG reviews the relevant data, including unblinded data (if deemed necessary by the SRG request), and will decide whether it is safe to suspend dosing or continue dosing at either the planned or alternative dose levels or decides to prematurely terminate the study:

1. Two or more subjects in any single cohort or across more than 1 cohort experience the same type of serious or medically significant event as defined by the Investigator
2. Two or more subjects in any single cohort or across more than 1 cohort experience alanine aminotransferase (ALT) and/or aspartate aminotransferase (AST) elevations $>5 \times$ upper limits of normal (ULN) in the absence of a concomitant bilirubin increase (see point 3 below)

3. One or more subjects in any single cohort or across more than 1 cohort experience ALT and/or AST elevations $>3 \times \text{ULN}$ in the presence of a total bilirubin increase $>2 \times \text{ULN}$ or an international normalized ratio (INR) >1.5 without findings of cholestasis or other alternate etiology to explain the elevations (i.e., “Hy’s Law cases”)
4. Two or more subjects in any single cohort or across more than 1 cohort experience ALT and/or AST elevations $>3 \times \text{ULN}$ with the appearance of fatigue, nausea, vomiting, right upper quadrant pain or tenderness, fever, rash, and/or eosinophilia ($>5\%$).

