If all doses are tolerated, then additional cohorts with higher doses may be considered. The actual choice of the subsequent dose level will occur after the full review of the available blinded safety, tolerability, clinical laboratory results, and available PK data in the preceding cohort. The subsequent dose level may be higher, lower, or remain the same as the prior dose level. If necessary, additional cohort(s) may be added to fully characterize the safety and tolerability of CVN766.

Initiation of the multiple-dose regimen will only occur after a full blinded review of all available safety, tolerability, and clinical laboratory results for the fasting drug administration to single-dose Cohort S3 (minimally including samples collected through Day 4) and available PK data. For each multiple-dose cohort after the first, the actual choice of dose level may be modified by the SRG after a review of the available blinded safety, tolerability, and clinical laboratory results, and available PK data in the preceding multiple-dose and next-higher-dosage single-dose cohorts (i.e., multiple-dose Cohort M2 will not initiate until the data review for multiple-dose Cohort M1 and single-dose Cohort S4 is complete). Each subsequent dose level may be higher, lower, or remain the same as the preceding dose level.

Additional multiple-dose cohort(s) may be added if deemed necessary by the SRG to fully characterize the safety and tolerability of CVN766. Such additional cohorts will follow the same schedule of events as for prior multiple-dose cohorts. Additional/Alternative PK timepoints may be implemented if the SRG determines this is necessary to fully characterize the PK profile of CVN766.

All AEs reported during the Treatment Period, both within and across cohorts, up to the time of discharge, will be evaluated to assess the need for the subject and/or study termination in accordance with the prespecified criteria for discontinuation/termination (**Section 6.3.1**).

Additionally, the SRG may decide not to escalate the dose for a particular cohort but rather administer the same or a lower dose level to the next cohort. Additional/ Alternative PK timepoints may be implemented if the SRG determines this is necessary to fully characterize the PK profile of CVN766.

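### Section 6.3.1 requires no dosing hold after a single death, life-threatening event or drug-related non-hepatic SAE; the gap lies mainly in the next daily dose within a multiple-dose cohort

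*Protocol*

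**What the plan says.** Section 6.3.1 names four events on which dosing must stop until the SRG has reviewed the data. Criterion 1 covers serious and medically significant events in general: "Two or more subjects in any single cohort or across more than 1 cohort experience the same type of serious or medically significant event". Criteria 2 to 4 concern ALT and AST. Criteria 2 and 4 need two subjects. Criterion 3, the Hy's Law rule, needs only one: "One or more subjects in any single cohort or across more than 1 cohort experience ALT and/or AST elevations" above the stated multiple, with raised bilirubin or INR and no other explanation.

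The two-subject rule appears twice more, each time limited to one cohort: in 6.1.3 ("If 2 or more subjects in a single cohort experience the same type of serious or medically adverse event") and in the Safety Review Group part of the synopsis ("if 2 or more subjects in a single cohort experience the same type of serious or medically significant event").

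The protocol also has more general provisions. The opening of 6.3.1 lets the study be stopped if the SRG or the IRB "considers the risk is no longer acceptable for subjects participating in the study". Section 6.1.3 has the SRG review each cohort's safety, laboratory and "available PK data to determine whether dosing should stop or continue". It also requires adverse events within and across cohorts, up to discharge, to be evaluated for possible subject or study termination "in accordance with the prespecified criteria for discontinuation/termination", pointing to 6.3.1. For the multiple-dose part, 6.1.2 says that "sentinel dosing within cohorts is not required in the multiple-dose regimen".

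**The concern.** This is a first-in-human trial whose primary objective is safety and tolerability. The purpose of 6.3.1 is to turn a decision to pause into a rule. It does so for one Hy's Law case but not for one death, one life-threatening event or one drug-related non-hepatic SAE, and the protocol does not explain the difference. Because criterion 1 also asks for the same type of event, two grave events of different types would not meet it either.

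At stake are the other subjects in the cohort. In a multiple-dose cohort they are dosed daily without a required sentinel. The protocol as written allows their next dose to be given before the SRG has reviewed a grave event in one of their number.

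**Working it through.** The protocol gives no trigger probability and no SAE rate, so there is no figure of its own to reproduce, and I assume no rate. The check has two parts.

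**Does any other provision require a pause after one event?**

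- 6.3.1, opening clause: has no subject count, but depends on a judgement that the risk is unacceptable.
- 6.1.3, evaluation of all adverse events up to discharge: a real duty that covers single events during the inpatient period. It measures them against the 6.3.1 criteria, so it leads back to the two-subject rule or to the opening clause. It imposes no pause of its own.
- 6.1.3, SRG review of whether dosing stops or continues: also without a two-subject threshold, but without timing. The only timed multiple-dose review is for escalation, at least 48 hours after the 7th dose, when dosing under the planned schedule is over.
- 6.3.3 and 8.5: the sponsor, IRB/IEC or regulator may suspend, and escalation may be interrupted. Both are options.
- 7.5: stops the affected subject only.
- 8.1.3 and 13.2: the Investigator supervises all dosing and may depart from the protocol to remove an immediate hazard. Neither requires a pause.
- 9.8.2: the SAE form is due within 24 hours. That equals the dosing interval, so timely reporting does not ensure review before the next dose.

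None of these requires a pause before the next dose.

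**How many doses could be affected?**

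Inputs: 8 subjects per multiple-dose cohort, 6 active and 2 placebo, dosed daily for 7 days (6.1.2). I assume that all 8 share one dosing calendar and have taken that day's dose when the event occurs on Day k.

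Doses still scheduled for the others = 7 × (7 − k). If the affected subject was on active drug, 5 of the other 7 are on active drug, so active doses = 5 × (7 − k). If the affected subject was on placebo, the multiplier is 6.

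| Event day | All doses | Active, affected subject on drug | Active, affected subject on placebo |
|---|---|---|---|
| 1 | 7 × 6 = 42 | 5 × 6 = 30 | 6 × 6 = 36 |
| 4 | 7 × 3 = 21 | 5 × 3 = 15 | 6 × 3 = 18 |
| 6 | 7 × 1 = 7 | 5 × 1 = 5 | 6 × 1 = 6 |
| 7 | 0 | 0 | 0 |

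These are ceilings that apply if nobody acts. If dosing stops before the next dose, the number is 0. If it stops after one further dosing day (an assumed lag), it is 7 × 1 = 7, of which 5 or 6 are active.

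In the single-dose cohorts the exposure is smaller. Sentinels are observed for 24 hours, each subject takes one dose (cohort S3 takes a second, no sooner than 14 days later), and escalation needs SRG review.

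**The case against.** The strongest reply is that a pause would happen anyway. Multiple-dose subjects are inpatients throughout dosing. The Investigator supervises every dose and is a named SRG member, so an SRG member would normally know of a grave event before the next dose. Each multiple-dose level will already have been studied or exceeded as a single dose (6.2). The top planned dose of 250 mg is about 15% of the 1670 mg/day that 6.2 gives as the maximum dose (250/1670 = 0.15). Criterion 1 also counts across cohorts: a first serious event in a multiple-dose cohort does trigger the hold if a like event occurred earlier in any cohort. Finally, nothing here contradicts another part of the protocol. It is a design choice.

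Most of this stands, and it limits the size of the point. It does not close the gap. One member knowing of an event is not a review, and prior single doses do not exclude toxicity that appears on repeat dosing. Cross-cohort counting does not help with the first event of its kind.

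A reader might infer that the protocol lets dosing run on after a death with nothing to stop it, or that 42 further doses are to be expected. The documents support neither. The duty to evaluate all adverse events, the SRG's stop-or-continue review and the opening clause of 6.3.1 all apply to a single event, and 42 doses would need six days of inaction in a supervised unit.

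**Conclusion.** The point holds in limited form. For non-hepatic serious events, the only mandatory hold needs two or more subjects with the same type of event, within or across cohorts. A single death, life-threatening event or drug-related SAE outside the liver rules, with no earlier like event, leaves the pause to judgement.

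The practical gap is the next daily dose or doses of the other 7 subjects in a multiple-dose cohort: realistically 0 to 7, with 42 as a theoretical ceiling after a Day 1 event in the planned 7-day schedule. The realistic range rests on the assumption that those on site stop dosing at the latest after one further dosing day. The counts also assume a shared dosing calendar. How often such an event would occur cannot be said from the protocol.

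The change is worth making because it is cheap and protects subjects, and because criterion 3 already accepts a single-case trigger. The gap does not undermine the design as a whole.

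**What to change.** Add one criterion to 6.3.1 and carry it into 6.1.3 and the synopsis. Further dosing is withheld pending SRG review after any one subject has:

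- (a) a death or life-threatening event, whatever the attributed cause; or
- (b) an SAE assessed as related to study drug under 9.7.6.

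Keep the two-subject rule for other serious or medically significant events, and leave criteria 2 to 4 as they are.

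Do not exempt events attributed to a study procedure. Limb (b) already requires a relation to study drug, so an exemption would act only on limb (a). There it would waive the hold after a fatal lumbar-puncture complication while keeping it after a death unrelated to either drug or procedure.

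The cost is one sentence in three places, using the existing SRG, the 24-hour SAE form and the drug-causality field already collected. The downside is an occasional short pause for an event that proves unrelated or occurred on placebo (2 of 8 subjects per cohort). Limb (b) can also be set off by lesser events, because 9.7.6 counts as related any event where drug involvement can be argued and 9.7.4 includes important medical events. A pause may interrupt the 7-day sequence and the steady-state PK of that cohort. The hold is temporary, and the SRG can release it as soon as it has reviewed the event.
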